This study is a double-blind, randomized, placebo-and positive-controlled, stratified parallel group clinical trial. A total of 192 patients diagnosed with DHS and meeting all necessary requirements for selection as subjects will be stratified into three balanced groups (64 per group) according to age, gender, and their mean sensitivity to cold air stimulus as scored on a Visual Analog Scale (VAS) at the time of baseline examination for final selection during the recruitment screening process. Males and females aged between 20 and 80 years will be enrolled. The three groups will be randomly assigned to use one of three test toothpastes having an identical base formulation but containing respectively either 0% nano-HAP (placebo), 15% nano-HAP or 5% KNO_3 (positive control). Subjects will be instructed to use their assigned test toothpaste as their sole oral hygiene product for the 8 weeks treatment duration. Subjects will be instructed to brush their teeth twice daily for 3 minutes, in the morning and before bed at night, applying on each occasion a one-inch strip of their assigned toothpaste on a soft-bristled toothbrush which will be supplied. Examination for DHS will include response to cold air, as the primary stimulus, and to tactile pressure, as a secondary stimulus, and will be conducted at the commencement of

recruitment screening (preliminary examination), then subsequently at baseline, 4 and 8 weeks. All dental examinations for data collection in all 192 subjects will be conducted by the same Clinical Examiner throughout the study. Subjects will be examined and queried on adverse events at each study visit.

POPULATION AND INITIAL SCREENING PROCEDURES

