This study will be conducted at the clinical research facility of the school of dentistry of the University of Texas Health Science Center at San Antonio (UTHSCSA) following approval by the UTHSCSA Institutional Review Board (IRB). UTHSCSA IRB will also approve the Human Assurance Documents as well as perform the compliance assessment (study monitor). All documents for this study will be used with Japanese language superimposed and will be approved by the IRB. This study will be conducted according to the "Recommendations for Evaluating Agents for the Reduction of Dentinal Hypersensitivity" as proposed by the Council on Dental Therapeutics of the American Dental Association, and in compliance with International Conference on Harmonization (ICH) Good Clinical Practice Guidelines including ICH E6, the Abbreviated Requirements of the Investigational Device Exemption Regulations (21CFR Part 812), and with 21 CFR Parts 50, 54, and 56.

Patients presenting to any of the dental school clinics, either with a primary complaint of tooth hypersensitivity or whom a clinician discovers to have a hypersensitive tooth or teeth during other routine dental treatment or examination will be screened to determine whether they meet study entry criteria.

Patients can be referred to the study Investigators by any of the dental school clinics or from surrounding private clinics. Initial screening of patients to confirm eligibility to participate in the study will be conducted by the Study Coordinator, and will include a medical history and information on medication use, and a review of the rest of the inclusion/exclusion criteria. 192 adult male and female patients, who are in good general health except for the symptoms of DHS, and who meet specific inclusion/exclusion criteria and the subsequent requirements of recruitment screening will be enrolled as subjects in the clinical study and randomized into the three test groups. The enrolment objective will be to have at least 57 subjects complete the study in each of the three test groups. Therefore to allow for about 10% dropout in each test group, 192 subjects (64 per group) will be enrolled. All relevant medical and non-medical conditions will be taken into consideration when deciding whether this protocol is appropriate for a particular subject. The following eligibility criteria are designed to select subjects for whom protocol treatment is considered appropriate.

Inclusion Criteria

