A total of 192 subjects diagnosed with DHS and who have met all necessary requirements for selection as subjects in the trial will be stratified into three balanced groups according to age, gender and VAS score in response to cold air stimulus at the time of baseline examination for final selection of subjects eligible to participate in the trial (64 per group). One of the three test products shall be randomly assigned to each of the three groups. The 0% and 15% nano-HAP-containing toothpastes and the 5% KNO₃ toothpaste shall be randomly coded as either A, B, or C by the manufacturer or Sponsor, and the code shall not be disclosed until all statistical analysis is complete.

Clinical Procedures

Immediately following the baseline sensitivity examination, each patient who qualifies to become a subject in the trial will be given and make the first use of his/her allotted test toothpaste, under the supervision of the Study Coordinator, after the latter has confirmed and recorded the weight of the tube. During the next 8 weeks, subjects will be required to brush their teeth twice daily with their allotted test product, as instructed, and not to take any food or drink for at least 30 minutes after brushing except for drinking water. A diary covering the duration of the study will be provided to each subject to (1) keep a record of number of times of brushing each day, and (2) record the name of any medication taken during the study period. All subjects will be asked to maintain their normal dietary habits. However, the use of oral hygiene products that are not related to this clinical trial, such as mouthwash and prescription medicine, along with dental clinic visits, dental treatment, professional plaque removal, whitening, use of pain relievers or commercial hypoallergenic products as well as use of narcotics, anti-inflammatory drugs, conventional analgesics, anticonvulsants, antihistamines, antidepressants, sedatives and other psychotropic drugs shall be prohibited throughout the course of the study.

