Comparisons among the three groups for differences in the primary and secondary efficacy outcomes at each time point will be analyzed using analysis of covariance; because of the stratified randomization, age, gender, and baseline VAS cold air sensitivity will be included as covariates. Pre-planned post-hoc comparisons include: 1) pair-wise comparisons of the test product and the positive control against the placebo, to demonstrate effectiveness and 2) 95% confidence intervals (CI) for the ratio of means for the nano-HAP test product to the positive control to demonstrate non-inferiority of the test product with the positive control. Non-inferiority will be demonstrated if the lower

bound of the 95% CI falls within the 20% non-inferiority margin. If the data are log-normally distributed, then the analyses will be done on the log-transformed data. If the 95% CI for the difference between the test paste and the positive control is transformed back to the original scale, the back-transformed CI is a 95% CI for the ratio of means. If data are normally distributed, the 95% CI will be computed using Fieller's theorem, and the other condition that must be met to show non-inferiority is that the reference (i.e. positive control) mean must be significantly different from zero using a one-sided test. A 5% significance level will be used for all tests. From the results obtained for the placebo and positive control groups, it will be confirmed whether the non-inferiority margin used in the trial (20%) was appropriate or not.

(2) Data Analysis for the Efficacy of the Secondary Evaluation Item

Repeated measures analysis of covariance will be used for comparison between the 4-week and 8-week outcomes within each group. Interactions of the treatment effect with age, gender, and tactile sensitivity will be examined to evaluate significance of differential effects of the treatment by patient characteristics.

Sample Size Calculation

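### The stated allocation rule makes the match of products to three balanced groups the only random step; it conflicts with other sections and cannot be carried out alongside dispensing at each subject's own baseline visit

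*Combined protocol and SAP*

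**What the plan says.** Two places set out how subjects reach a product, and both use the same two steps.

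- Summary of Study Design: the 192 subjects "will be stratified into three balanced groups (64 per group) according to age, gender, and their mean sensitivity to cold air stimulus". Then: "The three groups will be randomly assigned to use one of three test toothpastes having an identical base formulation".
- Randomization/Allotment to Test Product Groups: subjects "will be stratified into three balanced groups according to age, gender and VAS score in response to cold air stimulus". Then: "One of the three test products shall be randomly assigned to each of the three groups". The products are coded A, B or C by the manufacturer or sponsor, and the code stays closed until the statistical analysis is finished.

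Three other places point to randomization of subjects.

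- Population and Initial Screening Procedures: eligible patients "will be enrolled as subjects in the clinical study and randomized into the three test groups".
- The analysis section for the primary evaluation item: "because of the stratified randomization, age, gender, and baseline VAS cold air sensitivity will be included as covariates".
- Schematization of Test Design: randomization and group assignment are marked at the third visit, which is the baseline visit.

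Clinical Procedures fixes the timing: "Immediately following the baseline sensitivity examination, each patient who qualifies" is given the allotted toothpaste and uses it for the first time under supervision.

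**The concern.** In the section that a site would follow, chance enters only when three products are matched to three groups. Nothing there says that chance decides which group a subject joins. The sections that do speak of randomizing subjects name the act without giving a method.

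Both the non-inferiority comparison with KNO₃ and the superiority comparison with placebo depend on the arms differing only by chance before treatment. If group membership is settled by something other than chance, factors outside the balancing set may differ between arms. Examples are the number of test teeth, the extent of recession or erosion, and the tactile threshold within its entry limit. Such a difference would be fully confounded with product, since each product has a single group, and it could not be repaired after enrolment.

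**Working it through.** The question is one of procedure, so most of the check is a comparison of sections.

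1. **The plan's own figure.** Inputs from Sample Size Calculation: COV 0.5, ratio bound 0.80, true ratio 1.000, one-sided alpha 0.05, 10% dropout. On the log scale, SD = √ln(1 + 0.5²) = √0.2231 = 0.472, and the margin is −ln 0.80 = 0.223. The noncentral t calculation gives 57 per group with power 0.8056, matching the stated 57 and 0.80557. Then 57/0.9 = 63.3, rounded up to 64, and 3 × 64 = 192. The sample size reproduces, and this point does not change it.

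2. **What is random.** In both descriptions of the procedure, step one is stratification into balanced groups and step two is random assignment of products to those groups. Step one has no stated chance element. No section gives sequence generation, cut-points for age or VAS, a block size, a minimization rule, the person responsible, or concealment.

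3. **Consistency.** The screening section makes subjects the units that are randomized. The analysis section takes stratified randomization as given. The schedule places randomization at visit 3. None of these agrees with a rule in which only the product-to-group match is random.

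4. **Feasibility.** Forming three complete groups of 64 balanced on baseline VAS needs all 192 baseline scores. Clinical Procedures has each subject use the allotted paste directly after his or her own baseline examination. The first subject therefore needs an assignment when one of the 192 scores is known. Placement has to be made subject by subject, and no rule for doing so is given.

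5. **Consequence of following it literally.** Write the covariate-adjusted difference between two arms as τ + δ. Here τ is the product effect and δ is the difference in prognosis between the two groups that age, gender and baseline VAS do not explain. Under randomization of subjects, δ is a chance quantity, and the within-arm spread used by the ANCOVA measures its variability. Under the literal rule, δ is set by how the groups were formed, and the random match only decides which product carries it. With one group per product, nothing in the within-arm spread estimates δ, so the confidence interval does not allow for it.

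6. **Size of δ.** The documents give no data on unbalanced prognostic factors or on how groups would be formed. No value or defensible range follows from them.

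**The case against.** The strongest reply is that individual randomization was intended. Three sections say or imply it, and the Summary of Study Design calls the trial randomized. Because the group-first rule cannot be carried out, it is natural to read the groups as code letters: each subject is randomized to A, B or C at visit 3, and the products are separately allotted to the letters. The A/B/C sentence follows directly after the disputed one. This reading is plausible and may well be what was meant. It stands as a reason not to conclude that the trial lacks randomization. It does not remove the defect, because the dedicated section still states a different rule and no section supplies the method that this reading needs.

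The second reply is that harm is limited. The product code is closed, the trial is double-blind, the three balancing factors are also covariates, and entry requires a Yeaple value of 30 g or less. This holds in part. Someone who does not know the code cannot knowingly steer subjects to nano-HAP or KNO₃. But blinding to product does not make group membership random, and an entry limit narrows tactile differences without removing them.

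A reader might infer that site staff would place subjects by hand, with no chance element and no concealment. The documents do not say so. They are silent on the mechanism, and silence is an omission, not evidence of manual allocation.

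**Conclusion.** The point holds as a contradiction in a stated rule together with a missing method. The rule in the Summary of Study Design and in the randomization section would not randomize subjects if followed as written. It conflicts with three other sections, and it cannot be reconciled with dispensing straight after each baseline examination. The statistical consequence in step 5 is conditional: it applies only if groups are formed by something other than chance, which the documents neither establish nor exclude.

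The bias cannot be sized from the documents. A reader might count 3! = 6 product-to-group assignments and infer a smallest attainable p-value of 1/6. That is not supported. It treats all three products as exchangeable, whereas with placebo's group fixed only two assignments remain for nano-HAP against KNO₃. It also belongs to a randomization test that the plan does not use, since the plan specifies ANCOVA and a confidence interval for the ratio of means. Nor can a reader conclude that the arms will not rest on individual randomization; that is one reading of inconsistent text.

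The text should still be corrected before the first subject is allocated, because allocation underlies both main comparisons and cannot be redone later.

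**What to change.** Replace the two-step wording in the Summary of Study Design and in Randomization/Allotment to Test Product Groups, including the sentence that assigns products to groups. The new text should state that:

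- each eligible subject is individually randomized 1:1:1 at visit 3, after the baseline examination is complete and before the paste is dispensed;
- the schedule is computer-generated, using either permuted blocks within age, gender and VAS strata with stated cut-points, or minimization on those factors with a random element;
- someone not involved in enrolment prepares it, and each assignment stays concealed until it is made.

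With blocks or minimization, 64 per group becomes a target that the arms may miss slightly; the text should say so. The A/B/C coding can stay, described as a separate blinding step. Then align the screening section, the covariate rationale in the analysis section and the visit schedule with this method. If allocation has already begun, the report should describe the method actually used.

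The cost is protocol wording and preparation of a list. No extra subjects or visits are needed, and the sample size stands.

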Information concerning any adverse events will be obtained by the Clinical Examiner from the subjects at the time of sensitivity assessment. All observed or voluntarily reported adverse events regardless of test group or suspected causal relationship with a test product shall require immediate notification within 24 hours to the IRB and the Sponsor or its designated representative, during a reporting period beginning from the time that the subject first provides informed consent, which is obtained prior to the start of the clinical study, i.e. prior to the subject undergoing any study-related procedure and/or receiving any test product, through to and including 30 calendar days after the last administration of the test product. Any adverse event occurring any time after the reporting period must be promptly reported to assess whether it meets the criteria for classification as a serious adverse event requiring immediate notification to the Sponsor or its designated representative. The Principal Investigator is required to assess causality, and for all adverse events, sufficient information should be obtained by the Principal Investigator to try to determine the causality of the adverse event. For adverse events with a suspected causal relationship to a test product, follow-up by the Principal Investigator is required until the event or its sequelae are resolved or stabilized at a level acceptable to the Principal Investigator, and the Sponsor concurs with that assessment.

STATISTICAL PROCEDURES:

Product Efficacy Data Analysis:

Efficacy outcomes: The primary efficacy outcome will be the decrease in cold air stimulus sensitivity (VAS score) from baseline to 8 weeks. The secondary efficacy outcome will be the increase in tactile stimulus force from baseline to 8 weeks. Additional outcomes will include changes in cold air stimulus sensitivity and tactile stimulus force from baseline to 4 weeks.

(1) Data Analysis for Efficacy of the Primary Evaluation Item

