Subjects may withdraw from the trial at any time at their own request, or they may be withdrawn at any time at the discretion of the Principal Investigator or Sponsor for safety, behavioral, or administrative reasons. If a subject does not return for a scheduled visit, every effort should be made to contact the subject. In any circumstance, every effort shall be made to document subject outcome, if possible. The Principal Investigator should inquire about the reason for withdrawal, and request that the subject return all unused

test product, and return for a final visit, if applicable, and should also follow-up with the subject regarding any unresolved adverse events.

If a subject withdraws from the trial and also withdraws his/her consent for disclosure of future information, no further evaluations should be performed and no additional data should be collected. The Sponsor may retain and continue to use any data collected before such withdrawal of consent.

The Principal Investigator may discontinue a subject's participation if, in the opinion of the Principal Investigator, the subject is no longer a suitable candidate for the study. Possible reasons for such discontinuation include, but are not limited to:

- Adverse event
- Deviation from the protocol
- Missed appointment(s)
- Subject no longer meets eligibility criteria
- Use of antibiotic therapy or other prohibited medication during the study period

Criteria for Inclusion of Subjects as Appropriate for Efficacy Analysis

- Usage rate of toothpaste was 80% or more
- No evidence of events or activity likely to impair the reliability of the examination results, such as loss of diary records, etc.
- Subject has complied with the required restrictions during the examination period

Period of Data Storage :

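### One code letter per arm lets a single inferred product unmask 64 of 192 subjects; subject-level kit numbers would limit this to one

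*Combined protocol and SAP*

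**What the plan says.** The protocol's Summary of Study Design declares the masking: "This study is a double-blind, randomized, placebo-and positive-controlled, stratified parallel group clinical trial". It adds that the three pastes share an identical base formulation.

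The section Randomization/Allotment to Test Product Groups sets the level of the code. Three balanced groups of 64 are formed, and "One of the three test products shall be randomly assigned to each of the three groups". As for the code itself, the pastes "shall be randomly coded as either A, B, or C by the manufacturer or Sponsor, and the code shall not be disclosed until all statistical" work has finished. No separate code holder is named. Subject-level numbers, tube labels and a way of breaking the code for a single subject are not described.

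Under Clinical Procedures, the Study Coordinator weighs the first tube and supervises its first use. Subjects then bring their tube to each assessment visit for weighing and receive a second tube at week 4. The same Clinical Examiner carries out all examinations in all 192 subjects and, under Adverse Events, obtains the adverse-event information.

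On withdrawal, Criteria for Test Aborting and Drop-out says of subjects that "they may be withdrawn at any time at the discretion of the Principal Investigator or Sponsor for safety, behavioral, or administrative reasons".

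**The concern.** When a code has one value per arm, its secrecy is only as strong as its weakest single case. If one subject's product becomes apparent through a remark, a reaction or a property of the paste, anyone who can see the letters knows the product of every other subject with that letter. Even without a product name, a letter shows which subjects belong together, so a pattern of responses by letter can suggest what the letter stands for. The rule against disclosure covers release of the code. It does not prevent inference, and it does not bind whoever made the code.

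The primary endpoint is a self-reported pain score after a stimulus that the examiner delivers. The examiner may also, by judgement, apply a stimulus twice or include a sham test, and records the load at which the subject responds in the tactile test. One examiner takes every measurement, so if that person inferred a letter, a third of the data would be collected unmasked.

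A second, smaller gap concerns separation of roles. The Sponsor is permitted to make the code and is also permitted to withdraw subjects, and no text keeps the two apart.

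**Working it through.** **Inputs.** 57 evaluable subjects per group, 10% dropout, 64 enrolled per group and 192 in total (Sample Size Calculation); three letters, one product per group (Randomization/Allotment); one tube at baseline and one at week 4 (Clinical Procedures).

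**Plan's figure.** 57 / (1 − 0.10) = 63.3, rounded up to 64; 3 × 64 = 192. Both agree with the plan.

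**Exposure with one letter per arm**
- One letter inferred: 64 subjects, 64/192 = 33.3%. That is the subject concerned and 63 others.
- Two letters inferred: 2 × 64 = 128 directly. The remaining 64 follow by elimination, so all 192 are identified.

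**Exposure with a unique number per subject**
- One product inferred: 1 subject, 1/192 = 0.5%.

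**Labels needed.** 192 subjects × 2 tubes = 384.

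**Is there a practical route to the examiner?** The texts point both ways.
- For: tubes come to the same visits at which the examiner assesses sensitivity and asks about adverse events. The documents do not say who weighs the returned tubes at weeks 4 and 8, or that the examiner is kept from seeing them.
- Against: the Study Coordinator handles the tube at baseline, and no text shows the letter to the examiner.
- Base formulation: it is identical, but the products differ in the active ingredient (0% nano-HAP, 15% nano-HAP or 5% KNO3). The documents do not state that they are matched for taste, colour or texture.

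**Sponsor's position.** The coder is the manufacturer or the Sponsor, so Sponsor knowledge of the code is allowed but not stated. Withdrawal is at the discretion of the Principal Investigator or the Sponsor, for three kinds of reason, of which the administrative one is open-ended. The efficacy-inclusion criteria include a judgement on whether anything impaired the reliability of the results. No decision maker is named for it, and masking is not required. Nothing states that these decisions are made by people without the code.

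**The case against.** **Against the arm-level point.** Tube labels are not described, so a subject identifier might already be planned. The base formulation is shared, the examiner is not shown to see the letter, and the subject, not the examiner, marks the VAS line. All of this stands and lowers the probability of unmasking. It does not change what one unmasking would reveal. A subject number printed beside a product letter would not help either, because the letter would still be readable.

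**The stronger reading.** A reader might infer that the Sponsor could remove poor nano-HAP responders and so tilt the non-inferiority comparison. The documents do not support this. It would need three things during the trial: the code, each subject's letter and each subject's response.
- The first is only permitted, since the manufacturer may do the coding. No text gives the Sponsor the second.
- On the third, Period of Data Storage gives the Sponsor copies of study documents on completion. It mentions audits, but not that they occur mid-trial.
- Adverse events do reach the Sponsor promptly (they "shall require immediate notification within 24 hours to the IRB and the Sponsor or its designated representative"), but these are not VAS or tactile data. The Sponsor's concurrence concerns only whether a suspected product-related event has resolved or is "stabilized at a level acceptable to the Principal Investigator, and the Sponsor concurs with that assessment".
- Withdrawal is not the same as removal from the analysis. Withdrawn subjects are asked back for a final visit where applicable, and the efficacy-inclusion criteria do not list Sponsor withdrawal.

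For these reasons no inflation of the error rate is claimed. Any such figure would have to assume a selection mechanism that the documents do not show.

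**Conclusion.** The arm-level code is a weakness that is cheap to remove. On the plain reading of the allotment section, one inferred product exposes 64 subjects (33%) and a second letter exposes all 192, against one subject with individual numbers.

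This rests on two assumptions. The first is that the letter appears on the tube or is otherwise visible at the site. The second is that at least one subject's product could be inferred despite the shared base. Neither is stated in the documents, and neither is excluded.

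The missing separation between code holder and withdrawal or exclusion decisions is a secondary matter of clarification. The sample size and the planned tests are unaffected.

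**What to change.** **Main change, in Randomization/Allotment to Test Product Groups.** Replace the A/B/C code on tubes with a unique subject or kit number. Have the list linking numbers to products kept by a named code holder with no role in withdrawal, efficacy-exclusion, adverse-event review or analysis decisions. Define the holder by function: the documents do not say that the manufacturer is independent of the Sponsor, so naming the manufacturer alone would not settle the point. The record of which subjects form each group should stay with the same holder, because group membership carries the same information as a letter. The existing rule that the code stays closed until analysis is complete can remain if the holder gives the analyst masked group labels.

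**Secondary clarification, in Criteria for Test Aborting and Drop-out and in the efficacy-inclusion criteria.** State that non-safety withdrawals by the Sponsor and exclusions from the efficacy set are decided by personnel without access to the code, on documented grounds. Leave safety withdrawals as they are.

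**Cost.** About 384 individual labels, the upkeep of a kit list and a few sentences of protocol text. Sample size, visits and assessments do not change. If this separation and labelling are already intended, only the text is needed.
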